9.2 Baseline Visit Day -1

At the Baseline visit Day -1, if the subject's eligibility will be confirmed ¹ by the procedures shown in [Table 4](#). The subject eligible for randomization must abstain from any TNP, to ensure at least 23 hours of nicotine wash-out ahead of the IP exposure on Day 1.

¹ Alternate subjects will have to repeat the Baseline visit Day -1 to qualify for randomization. The data of that repeated visit will be captured in the database as "Baseline visit Day -1 – Second occurrence".

Confidentiality Statement

Data and information contained in this document are considered to constitute trade secrets and confidential commercial information, and the legal protections provided to such trade secrets and confidential information are hereby claimed under the provisions of applicable law. No part of this document may be publicly disclosed without the written consent of Philip Morris Products S.A.

Table 4 Time Schedule – Baseline Visit

| Time | Procedures | Additional Information |
|--------------------|---|---|
| Start of the Visit | Stop of TNP use | To ensure ≥ 23 hours of nicotine wash-out |
| During the Visit | TNP Use History questionnaire Information on smoking risks, advice on smoking cessation Concomitant disease / concomitant medication Body weight Vital signs ECG Spirometry Venous blood sample Spot urine sample | Smoking history Incl. THS briefing Since Screening visit BMI ≥ 5 min supine rest ≥ 15 min TNP abstinence ≥ 10 min supine rest ≥ 15 min sitting rest ≥ 1 hr TNP abstinence - Safety panel (hematology and clinical chemistry) - Safety panel - Drug test - Cotinine test - Pregnancy test (female) |
| | Alcohol breath test | |
| | Review of eligibility criteria | Incl. subject's willingness to comply with study procedures |
| | Randomization | |
| | AE/SAE recording | |

Abbreviations:

AE = Adverse event; ECG = electrocardiogram; hr = hour; Incl. = including; min = minute; SAE = Serious adverse event; TNP = tobacco and/or nicotine containing product.

9.3 Day 1

The study procedures performed on Day 1 are listed in [Table 5](#).

Table 5 Time Schedule – Day 1

| Time | Procedures | Additional Information |
|-------------|----------------------------|---------------------------|
| Prior to T0 | Vital signs | ≥ 5 min supine rest |
| Prior to T0 | VAS Craving T ₀ | ≤ 15 min prior to T0 |

Confidentiality Statement

Data and information contained in this document are considered to constitute trade secrets and confidential commercial information, and the legal protections provided to such trade secrets and confidential information are hereby claimed under the provisions of applicable law. No part of this document may be publicly disclosed without the written consent of Philip Morris Products S.A.

| | | |
|-------------------------|---|--|
| Prior to T0 | Blood sample T _B 0 | ≤ 5 min (± 2 min) prior to T0 |
| Just before T0 | Switch-on of THS (with stick) or lighting of CIG | Performed by investigational site staff |
| T0 | Start of IP use | |
| During / after IP use | Blood sampling (nicotine PK) | Post-T0 time points: T _B 1 after 4 minutes (± 1 min) T _B 2 after 6 min (± 1 min) T _B 3 after 8 min (± 1 min) T _B 4 after 10 min (± 1 min) T _B 5 after 12 min (± 1 min) T _B 6 after 15 min (± 2 min) T _B 7 after 30 min (± 5 min) T _B 8 after 1 hr (± 5 min) T _B 9 after 2 hrs (± 5 min) T _B 10 after 4 hrs (± 5 min) T _B 11 after 10 hrs (± 5 min) T _B 12 after 14 hrs (± 5 min) T _B 13 after 24 hrs (± 10 min) |
| | VAS Craving | Post-T0 time points T _v 1 after 4 min (± 2 min) T _v 2 after 10 min (± 2 min) T _v 3 after 15 min (± 2 min) T _v 4 after 30 min (± 2 min) T _v 5 after 10 hrs (± 5 min) |
| | VAS Liking and VAS Intention to Use Again | T _v 3 after 15 min (± 1 min) |
| ≤ 2 hours after T0 | Breakfast | |
| ≥ 4 hours after T0 | Lunch | |
| Ongoing | Nicotine wash-out Support during TNP abstinence period Concomitant disease / concomitant medication | Optional: snacks and water |
| | AE/SAE recording | |
| | Product events | Malfunction / misuse |

Abbreviations:

AE = Adverse event; CIG = combustible cigarette; hr(s) = hours; min = minute(s); IP = investigational product; PK = Pharmacokinetic; SAE = Serious adverse event; T0 = start of IP use; T_BX = time point blood sampling; T_vX = time point VAS assessment; THS = Tobacco Heating System; VAS = Visual analogue scale

Confidentiality Statement

Data and information contained in this document are considered to constitute trade secrets and confidential commercial information, and the legal protections provided to such trade secrets and confidential information are hereby claimed under the provisions of applicable law. No part of this document may be publicly disclosed without the written consent of Philip Morris Products S.A.

9.4 Day 2

The study activities performed on Day 2 are listed in [Table 6](#):

Table 6 Time Schedule – Day 2

| Time | Procedures | Additional Information |
|-----------------------|--|---|
| Prior to T0 | Vital signs | ≥5 min supine rest |
| Prior to T0 | VAS Craving T _V 0 | ≤15 min prior to T0 |
| ≤5 min prior to T0 | Blood sample T _B 14 | Day 1 sample T _B 13 (24 hrs ±10 min) = T _B 0 of Day 2 |
| Just before T0 | Switch-on of THS (with stick) or lighting of CIG | Performed by investigational site staff |
| T0 | Start of IP use | |
| During / after IP use | Blood sampling (nicotine PK) | Post-T0 time points: T _B 1 after 4 minutes (± 1 min) T _B 2 after 6 min (± 1 min) T _B 3 after 8 min (± 1 min) T _B 4 after 10 min (± 1 min) T _B 5 after 12 min (± 1 min) T _B 6 after 15 min (± 2 min) T _B 7 after 30 min (± 5 min) T _B 8 after 1 hr (± 5 min) T _B 9 after 2 hrs (± 5 min) T _B 10 after 4 hrs (± 5 min) T _B 11 after 10 hrs (± 5 min) T _B 12 after 14 hrs (± 5 min) T _B 13 after 24 hrs (± 10 min) |
| | VAS Craving | Post-T0 time points T _V 1 after 4 min (± 2 min) T _V 2 after 10 min (± 2 min) T _V 3 after 15 min (± 2 min) T _V 4 after 30 min (± 2 min) T _V 5 after 10 hrs (± 5 min) |
| | VAS Liking and VAS Intention to Use Again | T _V 3 after 15 min (± 1 min) |
| ≤2 hours after T0 | Breakfast | |
| ≥4 hours after T0 | Lunch | |

Confidentiality Statement

Data and information contained in this document are considered to constitute trade secrets and confidential commercial information, and the legal protections provided to such trade secrets and confidential information are hereby claimed under the provisions of applicable law. No part of this document may be publicly disclosed without the written consent of Philip Morris Products S.A.

| | | |
|---------|--|----------------------------|
| Ongoing | Nicotine wash-out Support during TNP abstinence period | Optional: snacks and water |
| | Concomitant disease / concomitant medication | |
| | AE/SAE recording Product events | Malfunction / misuse |

Abbreviations:

AE = Adverse event; CIG = combustible cigarette; hr(s) = hours; min = minute(s); IP = investigational product; PK = Pharmacokinetic; SAE = Serious adverse event; T0 = start of IP use; T_BX = time point blood sampling; T_VX = time point VAS assessment; THS = Tobacco Heating System; VAS = Visual analogue scale

9.5 Day 3

The study activities performed on Day 3 before and during IP exposure, and prior to the time of discharge are presented in [Table 7](#).

Table 7 Time Schedule – Day 3

| Time | Procedures | Additional Information |
|-----------------------|---|--|
| Prior to T0 | Vital signs | ≥5 min supine rest |
| Prior to T0 | VAS Craving T _V 0 | ≤15 min prior to T0 |
| ≤5 min prior to T0 | Blood sample T _B 14 | Day 2 sample T _B 13 (24 hrs ±10 min) ≡ T _B 0 of Day 3 |
| Just before T0 | Switch-on of THS (with stick) or lighting of CIG | Performed by investigational site staff |
| T0 | Start of IP use | |
| During / after IP use | Blood sampling (nicotine PK) | Post-T0 time points: T _B 1 after 4 minutes (± 1 min) T _B 2 after 6 min (± 1 min) T _B 3 after 8 min (± 1 min) T _B 4 after 10 min (± 1 min) T _B 5 after 12 min (± 1 min) T _B 6 after 15 min (± 2 min) T _B 7 after 30 min (± 5 min) T _B 8 after 1 hr (± 5 min) T _B 9 after 2 hrs (± 5 min) T _B 10 after 4 hrs (± 5 min) T _B 11 after 10 hrs (± 5 min) |

Confidentiality Statement

Data and information contained in this document are considered to constitute trade secrets and confidential commercial information, and the legal protections provided to such trade secrets and confidential information are hereby claimed under the provisions of applicable law. No part of this document may be publicly disclosed without the written consent of Philip Morris Products S.A.

| | | |
|-------------------------|--|---|
| | VAS Craving | Post-T0 time points Tv1 after 4 min (\pm 2 min) Tv2 after 10 min (\pm 2 min) Tv3 after 15 min (\pm 2 min) Tv4 after 30 min (\pm 2 min) Tv5 after 10 hrs (\pm 5 min) |
| | VAS Liking and VAS Intention to Use Again | Tv3 after 15 min (\pm 1 min) |
| Ongoing | Support during TNP abstinence period | |
| \leq 2 hours after T0 | Breakfast ECG Spirometry Venous blood sample Spot urine sample | \geq 10 min supine rest \geq 15 min sitting rest - Safety panel hematology and clinical chemistry - Safety panel - Pregnancy test (female) |
| \geq 4 hours after T0 | Lunch Vital signs Concomitant disease / concomitant medication AE/SAE recording Product events Information on smoking risks, advice on smoking cessation Discharge | \geq 5 min supine rest Malfunction / misuse Incl. THS briefing Stop of TNP abstinence |

Abbreviations:

AE = Adverse event; CIG = combustible cigarette; ECG = electrocardiogram; hr(s) = hours; IP = investigational product; min = minute(s); PK = Pharmacokinetic; SAE = Serious adverse event; T0 = start of IP use; TbX = time point blood sampling; TvX = time point VAS assessment; THS = Tobacco Heating System; TNP = tobacco and/or nicotine containing product; VAS = Visual analogue scale

9.6 Safety Follow-up Period

All subjects participating in the Baseline visit will enter a 3-day Safety follow-up (SFU) period at the time of Discontinuation from the study, even if they are not randomized into the study, unless they are Lost to follow-up.

After Discharge on Day 3, or after Early termination, the subject will enter a 3-day SFU period. During this 3-day period, there will be spontaneous reporting by the subject of new AEs and new SAEs. Any ongoing AEs/SAEs will be actively followed-up by the site. The SFU period is concluded by a phone contact to the subject on the last day of the SFU period.

Confidentiality Statement

Data and information contained in this document are considered to constitute trade secrets and confidential commercial information, and the legal protections provided to such trade secrets and confidential information are hereby claimed under the provisions of applicable law. No part of this document may be publicly disclosed without the written consent of Philip Morris Products S.A.

Any AEs or SAEs that are ongoing at the end of the 3-day Safety Follow-up period will be managed as described in Section [8.2.6](#).

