4.4 Study Duration

The entire study per subject will last up to 34 days. This will include a screening period of up to 27 days prior to Admission (Day -28 to Day -2), 4 days of confinement (from admission on Day -1 to time of Discharge on Day 3 (3 overnight stays), and a 3-day SFU period (from time of Discharge on Day 3 or Early termination plus three days). The end of the study (EOS) for a subject is defined as the end of the SFU period. The end of the whole study corresponds to the individual EOS of the last subject.

Confidentiality Statement

Data and information contained in this document are considered to constitute trade secrets and confidential commercial information, and the legal protections provided to such trade secrets and confidential information are hereby claimed under the provisions of applicable law. No part of this document may be publicly disclosed without the written consent of Philip Morris Products S.A.

5 Study Population

Thirty healthy female or male adult subjects who have smoked on average at least 10 regular CIG per day for the last 4 weeks prior to Baseline Day -1 will be randomized to one of 6 possible full crossover sequences of IP use (THS with either regular or menthol stick, and CIG) on Day 1 to Day 3. Quotas will be applied to ensure that the randomized population contains at least 40% of both sexes (i.e., at least 12 males and 12 females in the study) overall.

The subjects must have been smoking for at least 3 years prior to the Screening visit. There will be no brand restrictions of CIG. Smoking status will be verified with a urinary cotinine test (cotinine ≥ 200 ng/mL).

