8.2 Collection and Reporting of Adverse Events

8.2.1 Collection of Information

AEs should be collected mainly via face-to-face interview with the subject by the use of consistent, open, non-directive questions from the investigator(s) or designee(s) (e.g., “How have you been feeling since you were last asked?”).

Any non-serious AE occurrence during the study must be documented in the subject's medical records in accordance with the Investigator's normal clinical practice and on the AE page of the CRF. SAEs that occur during the study must be documented in the subject's medical record, on the AE CRF, and on the SAE form for recording into safety database.

Information recorded for AEs/SAEs will include verbatim description, start and stop dates, seriousness, severity (intensity), causal relationship with IP and study procedures, expectedness, action taken with IP (e.g., reduced, not changed), other action taken (e.g., treatment administered, if led to the subject's discontinuation from the study), and outcome (e.g., resolved, stabilized).

Whenever a medically meaningful diagnosis is available to comprise a set of reported signs and/or symptoms, it should be preferentially provided as the AE or SAE term, rather than the individual signs and/or symptoms.

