8.2.2 Period of Collection

AEs (including SAEs) will be collected from the time of ICF signature until the individual EOS for each participant.

Any AEs which occur during the Screening period will be captured by the investigational site staff and assessed by the Investigator or designee(s) to establish relationship to study procedures.

During a 3-day SFU period new AEs/SAEs will be recorded and ongoing AEs/SAEs will be followed-up by the study site, as described in Section [8.2.6](#).

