8.2.6 Follow-up of Non-serious and Serious Adverse Events

Any non-serious AE that is ongoing at the time of Discharge or early termination will be followed-up by the Investigator during the Safety follow-up (SFU) period until it has been resolved, stabilized (i.e., no worsening of the condition), or an acceptable explanation has been found (e.g., a chronic condition). The follow-up of the ongoing non-serious AEs will be done via a phone call performed at the end of the SFU period. If the subject does not respond at the first phone call, two additional attempts will be made, then subject will be declared lost to follow-up.

At the end of the 3-day SFU period, all ongoing non-serious AEs will have the outcome documented as “unknown” and will not be followed-up by the Investigator. At the discretion of the Investigator, the subject will be referred to his General Practitioner to have his/her ongoing AEs addressed accordingly.

All SAEs will be followed up by the Investigator or designee after the end of the SFU period, until their resolution, stabilization (i.e., no worsening of the condition), or an acceptable explanation has been found (e.g., a chronic condition). In case the subject cannot

Confidentiality Statement

Data and information contained in this document are considered to constitute trade secrets and confidential commercial information, and the legal protections provided to such trade secrets and confidential information are hereby claimed under the provisions of applicable law. No part of this document may be publicly disclosed without the written consent of Philip Morris Products S.A.

be reached for additional information related to SAE(s), a total 3 attempts should be performed before the subject will be declared as lost to follow-up.

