**Table IAEQ Overall Product Use Emergent Adverse Events (Safety Population)**

Adverse Event	Admission (N=X)	Product Administration				SFU (N = X)
		P1R (N = X)	P1M (N-X)	CIG (N = X)	Overall (N = X)	
Number of Subjects With PUEAEs	XX (XX%)	XX (XX%)	XX (XX%)	XX (XX%)	XX (XX%)	XX (XX%)
Number of Subjects With SAEs	XX (XX%)	XX (XX%)	XX (XX%)	XX (XX%)	XX (XX%)	XX (XX%)
Number of Subjects With IP Events	XX (XX%)	XX (XX%)	XX (XX%)	XX (XX%)	XX (XX%)	XX (XX%)
Number of Subjects With AEs Leading to Discontinuation	XX (XX%)	XX (XX%)	XX (XX%)	XX (XX%)	XX (XX%)	XX (XX%)
Number of Subjects With AEs Leading to Death	XX (XX%)	XX (XX%)	XX (XX%)	XX (XX%)	XX (XX%)	XX (XX%)
Number of Subjects With AEs Related to IP	XX (XX%)	XX (XX%)	XX (XX%)	XX (XX%)	XX (XX%)	XX (XX%)

P1R: THS regular stick  
 P1M: THS menthol stick  
 CIG: Combustible cigarette  
 Although a subject may have had 2 or more adverse events, the subject is counted only once within a category. The same subject may appear in different categories.  
 PUEAEs = Product use-emergent adverse events; SAEs = Serious adverse events; IP = Investigational product  
 Admission = after ICF and prior to the product test on Day 1  
 SFU = after discharge from CRU to safety follow-up visit  
 Source: Table 14.3.1.1  
 Program: /CAXXXX/sas\_prg/stsas/intext/t\_ae.sas DDMMYYYY HH:MM

Philip Morris Products S.A.  
 THS Induction device and regular or menthol sticks, P1-PK-12  
 [REDACTED] CA39924

In-text Shell IAES will be in the following RFT format:

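### New adverse events in the 3-day safety follow-up are left to spontaneous reporting, and no text has the closing telephone call ask about them, so a low SFU percentage cannot be read as reassurance.

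*Protocol*

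**What the plan says.** Protocol 8.2.1 sets the general method: "AEs should be collected mainly via face-to-face interview with the subject by the use of consistent, open, non-directive questions". Protocol 8.2.2 runs collection from consent to the subject's end of study and adds: "During a 3-day SFU period new AEs/SAEs will be recorded and ongoing AEs/SAEs will be followed-up by the study site". It does not say how new events are to be elicited.

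Protocol 9.6 does say. For new events: "During this 3-day period, there will be spontaneous reporting by the subject of new AEs and new SAEs". For events already open: "Any ongoing AEs/SAEs will be actively followed-up by the site". It then closes the period: "The SFU period is concluded by a phone contact to the subject on the last day of the SFU period". Section 8.2.6 describes what that call does: "The follow-up of the ongoing non-serious AEs will be done via a phone call performed at the end of the SFU period".

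SAP 8.8 summarizes SFU events separately from those under each product. The AE shells IAEO (labelled IAEQ where the shell is printed), IAES, CAEO, CAES and CAEE give the SFU its own count-and-percentage column beside P1R, P1M, CIG and Overall. The footnote to that column reads: "SFU = after discharge from CRU to safety follow-up visit". No footnote mentions how SFU events are ascertained, and the column's N is not defined.

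**The concern.** Section 9.6 contrasts two methods within the same paragraph: passive for new events, active for ongoing ones. This is a stated collection rule, not just an omitted detail. A site that followed 9.6 and 8.2.6 to the letter could close a subject's follow-up without asking how the subject had felt since discharge.

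AE incidence is a named secondary endpoint (Protocol 3.2). Spontaneous reporting is likely to miss mild events that open questioning would find. A small SFU percentage would then mix two explanations, few events and few questions, and the tables give the reader no way to separate them. The footnote adds to this by referring to a follow-up visit, although the protocol schedules only a telephone contact.

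**Working it through.** **Inputs**
- Study duration of up to 34 days: screening up to 27 days, confinement 4 days, SFU 3 days (Protocol 4.4).
- At least 24 h between product uses (Protocol 4.1), so the first T0 to the Day 3 T0 is about 48 h.
- Last Day 3 blood sample at T0 + 10 h (Protocol 4.1), taken as the earliest discharge. Discharge is on Day 3 after a morning T0, so *h*, the hours from the Day 3 T0 to discharge, is varied from 10 to 18. The upper end is an assumption.
- SFU of 3 days = 72 h.

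**The plan's own figure.** 27 + 4 + 3 = 34 days, as stated.

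**Share of time after first use that falls in the SFU** = 72 / (48 + *h* + 72)

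| *h* (h) | Total (h) | SFU share |
|---|---|---|
| 10 | 130 | 55.4% |
| 12 | 132 | 54.5% |
| 14 | 134 | 53.7% |
| 16 | 136 | 52.9% |
| 18 | 138 | 52.2% |

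In calendar days, Days 1 to 3 against three SFU days, the share is 3/6 = 50%.

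The call is on the last SFU day, so collection may stop before 72 h. With *h* = 10, a call 58 h after discharge gives 58/116 = 50%, and a call at 48 h gives 48/106 = 45%.

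**After the last use.** With *h* = 10, the SFU is 72/82 = 87.8% of the time from the Day 3 T0 to the end of study. With *h* = 18 it is 72/90 = 80.0%.

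**Time at risk behind each column.** Assume 30 completers, five per sequence, and *h* = 10. Each product is then used by 10 subjects on each day. Person-hours per product are 10×24 + 10×24 + 10×10 = 580, or 580/30 = 19.3 h per subject. The SFU column covers 72 h per subject, 72/19.3 = 3.7 times as long.

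**What a zero would mean.** If 0 of 30 subjects report a new SFU event, the one-sided 95% upper bound on the reported rate is 1 − 0.05^(1/30) = 9.5%. If only a fraction *s* of affected subjects report, the bound on the true rate is 9.5%/*s*: 12.7% at *s* = 0.75, 19.0% at 0.50 and 38.0% at 0.25. The values of *s* are assumed; the documents give none.

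**The case against.** The strongest reply is that the sections, read together, already allow the call to ask. Section 8.2.1 is not limited to confinement and makes face-to-face contact the main route, not the only one. Section 8.2.2 has new SFU events recorded. Section 5.3 names the end-of-SFU call separately from ongoing AEs, and 9.6 schedules it for everyone. Section 8.2.6 may mention only ongoing events because follow-up is its subject. Appendix A marks AE recording at every visit, although its early-termination and follow-up columns cannot be told apart in the available text. All this stands as far as it goes: a site may well ask. But none of these places says that it must, and 9.6, the only section that names a method for new SFU events, names the passive one.

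Second, elapsed hours are a rough measure of safety information. The protocol takes a nicotine half-life of about 2 h (12.1.2). Ten hours on site after the Day 3 use is then five half-lives, with about 3% left (0.5^5), so most acute effects should appear before discharge. Subjects may also use any tobacco or nicotine product after discharge (6.2.4, 6.2.5), so even full questioning could not tie SFU events cleanly to a study product. Both points stand and limit what is at stake.

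Third, the 58 h on site should not be called actively questioned time. No section sets how often staff ask; Tables 5 and 6 list AE recording only as ongoing.

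**Conclusion.** The point holds as a modest defect in AE ascertainment that is cheap to correct. New SFU events are assigned to spontaneous reporting, no text has the call ask about them, and the affected period is about half of the planned time after first use. That share rests on discharge 10 to 18 h after the Day 3 T0 and on a full 72 h of follow-up; it is lower if the call comes early.

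Three stronger readings are tempting and are not supported:
- **That most post-exposure safety time is passively covered.** This is true only in elapsed hours with a full 72 h. In calendar days it is exactly half, and an early call takes it below half.
- **That the product comparison is biased.** SFU events go to their own category (SAP 8.8), and shell CAESR defines Overall as ending at discharge. P1R, P1M and CIG are compared on events from confinement.
- **That the SAP treats ascertainment as equal across columns.** It makes no such claim; it is silent, and the layout invites the comparison.

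The number of events that would be missed cannot be estimated from the documents.

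**What to change.** **Protocol 9.6 and 8.2.6.** State that at the end-of-SFU telephone contact the site asks every subject the open question given as an example in 8.2.1, covering the time since discharge, and records any new AE or SAE with its onset. Keep spontaneous reporting up to the call.

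**SAP shells IAEO, IAES, CAEO, CAES and CAEE.** Add a footnote that the SFU column rests on spontaneous reports plus one telephone inquiry over up to 3 days. Replace the reference to a follow-up visit. State the denominator: under 9.6, subjects who attended Baseline but were not randomized also enter the SFU, and they have used no study product.

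With the question added, no part of the SFU would depend on spontaneous reporting alone, although one recall question over up to 72 h is still weaker than repeated questioning on site.

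**Cost.** One question on a call already planned, plus wording in two protocol sections and five shells. A few more mild AEs may be recorded. Product use and the visit schedule do not change.
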